7.6.4 Day 6, Phone Contact: End of Study

Day 6, follow-up procedures by phone include:

Safety contact for evaluating any Adverse Events and the need or not for a safety extra visit as per Investigator judgement.

7.6.5 Unscheduled Visit

Unscheduled visits may occur for any reason if the subject or the investigator consider that it is necessary. The reason and the performed procedures will be collected in the CRF.

7.7 Follow-Up Procedures and Therapy Transitions

There are no longer-term follow-up or therapy transition procedures.

7.8 Study Timetable / Schedule of Events

Table 3. Schedule of Events

Visits	V1	At	V2	Phone	Unsch	Notes
		Home		Call		
Days	D1	D1 to	D5	D6		
		D5				
Eligibility verification	✓					
Informed Consent	✓					
Demographics /	✓					
Medical History						
Physical Exam	✓		✓		✓	
Vital Signs	✓				✓	

Visits	V1	At	V2	Phone	Unsch	Notes
		Home		Call		
Days	D1	D1 to D5	D5	D6		
Urine Pregnancy Test	√					For women of child-bearing potential only
E-diary Activation	✓					
Randomization	✓					
E-diary Completion	✓	√ *	√ **			*2 times per day at the same times **On-site evaluations
Pain perception	✓	✓	✓			
Pain-relief evaluation		✓	✓			
Pain acceptable perception		~	√			
Rescue Medication Needed		V	√			
Roland-Morris Disability Questionnaire	√		√			
Mobility assessment	√		√			Schober's Test or Fingertip- to-floor test
Adverse Event assessment	√	~	√	√	√	
Patch application / removal	✓		✓		✓	Patch(es) has(have) to be used for 5 days. If the patch is taken-off for a safety reason, the subject has to contact the study center. If the patch falls off, the subject has to replace it as soon as possible. The subject will complete the diary card, informing about the patch replacement, the reason of change, and the time spent with no patch.
Concomitant therapies	✓	✓	✓	✓	✓	
e-diary review			√		√	

7.9 Study Protocol Compliance / Treatment Adherence

Subject compliance to the protocol will be defined as

- Subjects comply with study visit schedule
- Subjects complete the e-diary as instructed

Subjects will be considered compliant if they complete at least 80% of the required e-diary entries, and attend all scheduled visits. Non-complaint subjects will not be replaced. Compliance to the e-diaries does not impact the primary endpoint, as that is determined as a change from baseline.

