6.3 Evaluation Criteria / Efficacy and Safety

6.3.1 Primary Efficacy Clinical Endpoint

A Numerical Rating Scale^[3] (NRS) responder at Day 5 at the on-site evaluation (defined as $\geq 30\%$ decrease from baseline of the instantaneous pain^[4] and no rescue medication)

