6.4.4.3 Rescue Medications

During the study, subjects can be treated with up to 2 g of Paracetamol per day (rescue therapy) to be documented in the e-diary. Any other analgesics and anti-inflammatory drugs as well as any non-pharmaceutical therapy are prohibited during the study duration, if a subject needs to use one of these options, it has to be documented in the e-diary.

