7.6 Clinical Procedures

The study will be performed in Investigational Sites and an online e-diary will be used.

A total of 2 site visits and 1 phone contact are planned during a maximum of 5 days of treatment and 6 days of total study duration.

7.6.1 Day 1, Visit 1

Clinical procedures on Day 1, Visit 1 include the following:

- Verification of eligibility
- Informed Consent Signatures
- Local Physical Examination

- Collection of Vital Signs to include: Respiratory rate, Heart rate, Temperature, Blood Pressure
- Collection of Demographics to include: Age, Gender
- Collection of relevant medical history and concomitant medications
- On-line daily e-diary will be explained and activated
- Urine pregnancy testing (for women of childbearing potential only)
- Causes and/or circumstances triggering the acute back pain
- Baseline Subject symptom self-assessment
 - Pain Perception (NRS): Numerical Rating Scale^[3] for pain assessments at baseline and at defined time points: 0-10 NRS; '0' representing "no pain" and '10' representing "worst pain imaginable
 - Instantaneous: pain at the moment of the evaluation
 - Average pain in the previous 12 hours.
 - Worst pain in the previous 12 hours
 - Least pain in the previous 12 hours
 - o Roland-Morris Disability Questionnaire (RMDQ)^[5]
- Baseline mobility assessment (physician)
- Randomization:
 - O Arm A: ITP FIRTECH: Patch application according to the instruction for use in Section 17.3: The patch has to stay in position for 5 days. If the patch is taken-off or if it fell off during the study duration, the subject is invited to replace the patch at home following the instruction for use. Subject is allowed to take-off the patch at any time in case of severe skin itchiness, irritation, or skin reaction and in this case the subject has to contact the study center.
 - o Arm B: no-patch: Subjects will be informed that they will not be assigned a patch in this study.
- All subjects are informed that rescue mediation (paracetamol, up to 2 g per day), while not encouraged, is allowed if necessary.
- All subjects will be informed of the prohibited medications.
- If rescue medication is taken, the exact moment(s) and the dose(s) have to be indicated in the e-diary.
- An explanation will be provided on how to use e-diary at home and providing all necessary access credentials
- All subjects will be requested to avoid bed rest and will be recommended to continue with a normal daily life activity.

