3.4 Analysis Timepoints for e-diary Questionaries

The analysis timepoints will be derived for questionaries collected via e-diary (for an extract based on Data Export Specification 2.0) as defined in Table 3.

The study day will be calculated as the following:

$$Study Day = (Completed Date) - (Randomization Date) + 1.$$

Adverse events, medication usage and patch application data collected via e-diary will not be used for analysis. Those are being transcribed by the site from the diary into the CRF database that will be used for analysis.

In consistency with Section 3.1, assessments collected at Day 1 Visit 1 will be considered as the baseline (if for FIRTECH Patch arm the assessment was done before the Patch application). Analysis timepoints "Baseline" and "Day 5 Visit 2" are derived only for on-site evaluations.

CONFIDENTIAL Page 14 of 30

Table 3: Analysis Timepoints for eDiary

Study Day	Questionnaire Name	Analysis Timepoints
Day 1ª	Daily Diary (Visit 1 Day 1) or Evening Daily Diary when Protocol Deviation (PD) comment completed as mentioned in the NTF number: 019, dated 22 Nov 2022 and when the associated PD occurrence date is equal to the CRF Visit 1 date.	Baseline
Day 1	Roland-Morris Disability Questionnaire	Baseline
Day 1	Evening Daily Diary	Day 1 Evening
Day 2	Morning Daily Diary	Day 2 Morning
Day 2	Evening Daily Diary	Day 2 Evening
Day 3	Morning Daily Diary	Day 3 Morning
Day 3	Evening Daily Diary	Day 3 Evening
Day 4	Morning Daily Diary	Day 4 Morning
Day 4	Evening Daily Diary	Day 4 Evening
Day 5	Morning Daily Diary	Day 5 Morning
Day 5 ^a	Daily Diary (Visit 2 Day 5) or	Day 5 Visit 2
	Morning Daily Diary when PD comment completed as	
	mentioned in the NTF number: 019, dated 22 Nov	
	2022 and when the associated PD occurrence date is	
	equal to the CRF Visit 2 date.	
Day 5	Roland-Morris Disability Questionnaire	Day 5 Visit 2

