5.1.7 Efficacy Analysis

5.1.7.1 Primary Analysis

Instantaneous pain on NRS will be summarized for actual values and change from baseline with descriptive statistics for the ITT and FAS populations by treatment group and by analysis timepoint (from Baseline to Day 5 Visit 2).

NRS-response will be defined as $\geq 30\%$ decrease from the baseline of the instantaneous pain and no rescue medication (Section 5.1.7.4.2).

CONFIDENTIAL Page 19 of 30

The number and percentage of NRS-responders at Day 5 Visit 2 will be presented descriptively by treatment groups, along with associated 95% confidence intervals.

The difference in the rate of responders at Day 5 Visit 2 will be tested between treatment groups using two-sided Fisher's exact test at the 5% error level (alpha = 0.05) and presented with its associated p-value. The null hypothesis H_0 that there is no difference in the rate of responders will be tested against the alternative hypothesis H_A that there is a difference in the rate of responders:

$$H_0: p_T - p_C = 0$$

$$H_A: p_T - p_C \neq 0$$

Where p_T denote the rate of responders at Day 5 Visit 2 in the FIRTECH Patch treatment group (treatment, T) and p_C denote the rate of responders at Day 5 Visit 2 in the No Patch treatment group (control, C). This analysis will be based on the mITT population.

A sensitivity analysis will be conducted by executing the primary endpoint analysis for subjects from the Sensitivity Analysis population. A list of subjects excluded from the Sensitivity Analysis population will be provided along with the reason for their exclusion.

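### Protocol 7.9 says e-diary compliance cannot affect the primary endpoint, but the no-rescue half of that endpoint is recorded in the e-diary

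*Protocol*

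**What the plan says.** On compliance, Protocol 7.9 says: "Compliance to the e-diaries does not impact the primary endpoint, as that is determined as a change from baseline". A subject counts as compliant with at least 80% of the required e-diary entries and attendance at all visits.

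The primary endpoint (Protocol 6.3.1, SAP 5.1.7.1) is a responder status with two parts: a decrease of at least 30% in instantaneous NRS pain at Day 5, "and no rescue medication". SAP 5.1.7.4.2 counts rescue from randomization to Day 5 Visit 2, plus rescue already ongoing at randomization.

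On where rescue is recorded, Protocol 6.4.4.3 says it is "to be documented in the e-diary", and the Visit 1 procedures in Protocol 7.6 say: "If rescue medication is taken, the exact moment(s) and the dose(s) have to be indicated in the e-diary". On what is analysed, SAP 3.4 says: "Adverse events, medication usage and patch application data collected via e-diary will not be used for analysis". It then explains: "Those are being transcribed by the site from the diary into the CRF database that will be used for analysis".

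The mITT set (SAP 4.1.2) requires an NRS value at baseline and at Day 5 Visit 2 and a baseline score above 0. It sets no condition on diary completeness. The FAS (SAP 4.1.3), used for all key secondary analyses, leaves out rescue users.

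**The concern.** The reason given in 7.9 fits the NRS part, which compares two on-site values. It does not fit the rescue part, which is a five-day history collected through the diary. If a subject takes rescue in a period whose diary is missing, and nothing later captures it, the CRF holds no rescue record. If pain has also fallen by at least 30%, that subject can be counted as a responder although the endpoint says otherwise. The same subject would wrongly enter the FAS.

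The trial is open label, so equal diary completion in the two arms cannot be taken for granted. Unequal under-recording would bias the primary comparison. Equal under-recording would dilute the difference if rescue use is higher in one arm.

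**Working it through.** 1. **Diary count.** At-home pain diaries: Day 1 evening, Days 2 to 4 morning and evening, Day 5 morning = 1 + 6 + 1 = 8. Adding baseline and Visit 2 gives 10 pain diaries, and 2 RMDQ forms make the 12 of SAP 5.1.7.5.1. Ten of 12 is 83% (compliant) and 9 of 12 is 75% (not). A compliant subject can thus miss 2 of 8 at-home entries (25%), about a day of rescue recording. Non-compliant subjects with both NRS values also stay in mITT.

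2. **Data path.** Rescue: e-diary, then site transcription, then CRF, then responder status. The SAP's use of CRF data adds a step but does not remove the dependence on the diary. NRS: only the baseline and Day 5 on-site values enter the endpoint. Missed at-home diaries leave both unchanged, and a missing on-site NRS removes the subject from mITT.

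3. **Size of a bias.** The documents give none of the inputs, so all are assumptions: r = share using rescue, q = share of rescue users with at least a 30% NRS fall, m = share of rescue users whose rescue goes unrecorded. The observed responder rate in an arm rises by r × q × m. With r and q equal in both arms, the bias in the difference is r × q × (difference in m).
   - r = 0.30, q = 0.5, m = 0.25 and 0.10: 0.30 × 0.5 × 0.15 = 0.0225, about 2.3 points.
   - r = 0.20 or 0.40: 1.5 or 3.0 points.
   - If each rescue user takes rescue in two independent diary periods and both must be missed: 0.25² − 0.10² = 0.0525, and 0.30 × 0.5 × 0.0525 = 0.0079, about 0.8 points.

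   The range is roughly 1 to 3 points. The differences in Table 2 of the protocol run from 17 to 21.

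4. **Effect on the planned test when the arms are equal.** Fisher's exact test, two-sided 5%, 90 per arm, true responder rate 40% in both: the exact rejection rate is 3.7%. As a harsher contrast, let m = 20% in one arm and 0 in the other, with r from 20% to 40% and q from 40% to 60%. The affected arm gains 0.2 × 0.4 × 0.2 = 1.6 to 0.4 × 0.6 × 0.2 = 4.8 points, or 1.4 to 4.3 false responders per 90. The rejection rate becomes 4.1% to 7.6%. With m = 20% in both arms it stays at 3.3% to 3.6%.

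5. **Effect when the patch works.** Take the 40% vs 61% row of Table 2. The pooled normal approximation at 90 per group gives 81.0% power, which reproduces the plan's 80%. The exact power of Fisher's test is 75.2%, the reference here. Assume rescue use of 40% without and 20% with the patch, and m = 20% in both arms.
   - q = 0.4: 0.40 + 0.4 × 0.4 × 0.2 = 43.2%; 0.61 + 0.2 × 0.4 × 0.2 = 62.6%. The difference is 19.4 points and power 68.2%.
   - q = 0.6: 44.8% vs 63.4%. The difference is 18.6 points and power 64.6%.

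   With the same rescue rates, under-recording only in the patch arm widens the 21-point difference to 22.6 or 23.4. Under-recording only in the no-patch arm narrows it to 17.8 or 16.2. The direction depends on which arm under-records.

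**The case against.** The strongest reply is that a false responder needs several failures together: a missed entry, no later capture, and a fall of at least 30%. Visit 2 works against this. The on-site entry asks about rescue with time and dose and about concomitant therapies, and the site verifies the diary (Protocol 7.6.3). The rescue question has no 12-hour recall limit, unlike the average, worst and least pain items, so a later entry can report an earlier dose. Protocol 10.3 requires missing CRF data to be explained and diary data to be checked for completeness. CRF version 4.0 is not among the documents reviewed and may already hold a yes/no rescue confirmation.

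Most of this stands, and it makes the event less likely. It does not close the gap, because neither document requires Visit 2 to resolve each missed period.

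Two stronger readings are tempting. A reader might infer that the SAP sets a rule that no record means no rescue. It does not: SAP 5.1.7.4.2 defines rescue as treatment received, and the SAP is silent on unknown status. A reader might also infer that missed diaries corrupt the NRS part. They do not, as step 2 shows.

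**Conclusion.** The sentence in Protocol 7.9 is incorrect for the endpoint as defined. Following the plan as written, an unrecorded rescue user can be counted as a responder and can wrongly enter the FAS.

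Neither size nor direction can be determined from the documents. The 1 to 3 points rest on assumed rescue use of 20% to 40%, half of rescue users meeting the NRS criterion, and missed shares of 10% and 25% by arm, with no recovery at Visit 2. These lean high: 25% as an arm average equals the most a compliant subject can miss at home, and any recovery at Visit 2 reduces the figure. The one-arm contrast in step 4 is harsher and reaches 4.8 points. A reader might infer a bias in favour of the patch, but nothing in the documents shows which arm would under-record. The point does not overturn the design, but it merits correction before database lock.

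**What to change.** - **Protocol 7.9:** delete or correct the sentence, so that it says missed at-home diaries leave the NRS part untouched but can affect the no-rescue part.
- **Visit 2:** use the existing e-diary verification to record yes/no rescue in the CRF for every missed diary period, where this is still possible. The note to file of 22 November 2022 cited in SAP 3.4 shows that some subjects had already passed Visit 2.
- **SAP 5.1.7.1, before database lock:** keep the primary responder definition. Add a sensitivity analysis that counts subjects with unresolved rescue status as non-responders, and report their number by arm. The existing sensitivity population (SAP 4.1.4) addresses only the on-site assessments recorded under the wrong diary form.

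A confirmed-no-rescue rule should not replace the primary definition. With 10% and 25% of entries missed independently, 1 − 0.90⁸ = 57% and 1 − 0.75⁸ = 90% of subjects would miss at least one of 8 at-home diaries. Any left unresolved would count against the arm with more missed entries.

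The cost is one CRF item, one extra table and slightly lower responder rates in the sensitivity analysis. That analysis can itself be distorted if missed diaries differ by arm, which is why the counts by arm belong beside it.

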7.10 Deviations from the Clinical Protocol

When a deviation from the protocol is identified for an individual subject, the investigator must document the deviation on a Protocol Deviation Form and contact the sponsor (or its acting representative). A description of the deviation from the protocol and justification must be recorded on the Protocol Deviation Form.

7.11 Subject Withdrawal

7.11.1 Subject Withdrawal

Subjects who withdraw (or are withdrawn) will not be replaced. Subjects may be withdrawn from the study for any of the reasons described in Section 6.4.7. Upon withdrawal, subjects will, if possible, be assessed by the Day 5 procedures for study exit. Termination of the study treatment does not affect subject safety, therefore no termination specific procedures are required. Termination of study treatment does not require any specific therapy or treatment transitions.

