6.4.1 Sample Size

The efficacy of the patch will be assessed compared with no-patch use. The primary endpoint is the occurrence of being a NRS-responder at Day 5 defined as \geq 30% decrease from baseline of the instantaneous pain and no rescue medication. The responder proportion in the "no-patch" arm is unknown, and a variety of proportions of responders are envisaged. The targeted treatment effect size is medium (Cohen's H ranging from 0.42 to 0.45). Ninety evaluable subjects per group (180 evaluable subjects in total) are needed to reach 80% power, as shown in the following table.

Alpha N per Group **Responder Rate** Cohen's H (2 sided) No Patch Patch 90 5% 10% 27% 0.449 90 5% 20% 39% 0.422 90 5% 30% 51% 0.432 90 5% 40% 61% 0.423 90 5% 50% 71% 0.433 90 0.422 5% 60% 80% Powers are calculated using East 6.4

Table 2. Power Calculations

Further assuming a dropout rate of 10%, the expected number of subjects to be randomized is a total of 200. Subjects will be randomized 1:1 to the treatment and no patch arms. The estimated number to be screened to achieve 200 randomized subjects is 260.

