6.4.7 Exit / Discontinuation Criteria

Subjects will exit the study if any of the following conditions exist:

- 1. Subject voluntarily withdraws from the study.
- 2. Subject death.
- 3. Subject is non-compliant with the protocol (as defined in Section 7.9)
- 4. Subject's well-being, in the opinion of the Investigator, would be compromised by study continuation.
- 5. Subject experiences an Adverse Event leading to voluntarily withdrawal and/or requiring withdrawal as per Investigator judgement.

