7.6.3 Day 5, Visit 2 Patch Removal / End of Treatment

Clinical procedures on Day 5, Visit 2 (Investigational Site) include the following:

- Completion of the e-diary on site
 - o Pain perception (using NRS)
 - Instantaneous: pain at the moment of the evaluation
 - Average pain in the previous 12 hours.
 - Worst pain in the previous 12 hours
 - Least pain in the previous 12 hours
 - Pain relief (Using VRS)

- o Is the Pain acceptable?
- o Need of rescue medication (time and dose)
- o Adverse Events
- o Concomitant therapies if any
- E-Diary verification
- Arm A Subjects: Patch is removed.
 - o Collection of all used and unused patches.
- Arm B Subjects: subjects are informed about the end of the evaluation period
- Local physical examination, including at patch localization (only for Arm A subjects)
- Vital signs
- Roland-Morris Disability Questionnaire (RMDQ)^[5]
- Mobility assessment (physician)

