4.1.2 Modified Intent-to-Treat (mITT) Population

The mITT population will be defined as all subjects randomized that had the NRS evaluation done at baseline and Day 5 Visit 2 with the exclusion of subjects without any pain at baseline (i.e. baseline instantaneous pain NRS score equal to "0"). This population will be used for the primary endpoint analysis.

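### Subjects who leave the study on Days 1 to 4 are not asked for a Day 5 rating, so they drop out of the primary analysis even when they could still give one

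*Protocol*

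**What the plan says.** Protocol 6.4.7 lists the conditions under which subjects exit the study. They include an adverse event that leads to or requires withdrawal, the investigator's view that continuing would compromise the subject's well-being, and "Subject is non-compliant with the protocol (as defined in Section 7.9". Section 7.9 defines compliance as at least 80% of required diary entries and attendance at all scheduled visits. It also says: "Compliance to the e-diaries does not impact the primary endpoint, as that is determined as a change from baseline".

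Protocol 7.11.1 is softer than 6.4.7: "Subjects may be withdrawn from the study for any of the reasons described in Section 6.4.7". It provides one assessment for these subjects: "Upon withdrawal, subjects will, if possible, be assessed by the Day 5 procedures for study exit". Section 7.11.2 keeps the data gathered before withdrawal, and 7.7 plans no further follow-up.

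On the analysis side, SAP 4.1.2 limits the primary population to "all subjects randomized that had the NRS evaluation done at baseline and Day 5 Visit 2", less those with no pain at baseline. SAP Table 3 assigns the Day 5 Visit 2 timepoint to on-site diary records on Study Day 5. It has no early-termination timepoint.

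**The concern.** The trial compares patch with no patch as randomised, lasts five days, and already has a site visit on Day 5. A subject who leaves on Day 3 for an adverse event or by investigator decision may still be able to give the primary pain rating two days later. The plan does not ask for it. The rating taken at exit does not replace it, because it is not a Day 5 rating and SAP Table 3 gives it no on-site timepoint.

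At stake is how close the primary comparison stays to the groups as randomised. In an open-label trial, exits may differ between arms and may be related to response. Excluding such subjects then moves the estimated difference, and a rating that could have been collected would have limited this. The exit reason based on diary completion is also hard to justify when 7.9 itself says that diary compliance does not bear on the primary endpoint.

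**Working it through.** **1. Path of a subject who exits on Day 3.** Protocol 6.4.7 makes it an exit from the study, not only from the patch. Section 7.11.1 gives one assessment on that day, if possible. SAP Table 3 needs an on-site record on Study Day 5, which does not exist. SAP 4.1.2 then removes the subject, and SAP 5.1.7.1 runs the primary Fisher test without them. There is no imputation or non-responder rule, and the only sensitivity population (SAP 4.1.4) is a subset of the same population. Even a subject who took rescue medication before exit, and so could not be a responder, leaves the denominator.

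**2. How many subjects.** Protocol 6.4.1: "Further assuming a dropout rate of 10%, the expected number of subjects to be randomized is a total of 200". Check: 180 / (1 − 0.10) = 200, so about 20 subjects are allowed to fall out for any reason. That allowance also covers voluntary withdrawal and death, so this route accounts for only part of it.
- *Diary non-compliance.* SAP 5.1.7.5.1 counts 12 diaries: 4 evenings (Days 1 to 4) + 4 mornings (Days 2 to 5) + 2 on-site + 2 RMDQ. Two missed is 10/12 = 83.3%; three missed is 9/12 = 75%, below the threshold. But the diary is checked on schedule only at Visit 2 ("E-Diary verification" in 7.6.3; "e-diary review" in the 7.8 table) or at an unscheduled visit.
- *Missed visit.* The only site visits are Visit 1 and Visit 2, so no visit can be missed between enrolment and Day 5.
- *Patch removal.* Section 7.6.1 lets a subject take the patch off for a skin reaction and contact the centre. This is not a listed exit reason.

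What remains is mainly exits for adverse events or by investigator judgement.

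**3. Power.** The planned 90 per arm reproduces with the pooled two-proportion formula, n = [1.960·√(2p̄(1−p̄)) + 0.842·√(p₁(1−p₁) + p₂(1−p₂))]² / (p₂−p₁)². At 20% v 39% (p̄ = 0.295) this gives (1.264 + 0.531)² / 0.0361 = 89.3, so 90, the largest of the six rows. The planned test is Fisher's, so the table gives exact two-sided Fisher power (%) at 5%. To 90 per arm at the Table 2 rates it adds 3 or 10 recovered leavers per arm (assumed numbers), under two assumptions about how they respond.

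| No patch v patch | 90 per arm | Leavers like their arm: 93 / 100 | Leavers at 20% in both arms: 93 / 100 |
|---|---|---|---|
| 10 v 27% | 80.5 | 82.1 / 85.0 | 79.2 / 75.6 |
| 20 v 39% | 76.1 | 77.3 / 80.7 | 74.7 / 72.2 |
| 30 v 51% | 78.9 | 79.2 / 83.2 | 76.7 / 74.8 |
| 40 v 61% | 75.2 | 77.5 / 82.7 | 74.7 / 74.2 |
| 50 v 71% | 79.4 | 79.7 / 83.3 | 76.4 / 74.7 |
| 60 v 80% | 80.2 | 81.3 / 84.4 | 77.8 / 72.6 |

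Under the first assumption power rises by 0.3 to 2.3 points at 93 per arm. Under the second it falls in every row, by 0.5 to 3.0 points at 93 and 1.0 to 7.6 at 100. Fisher discreteness makes single rows uneven: 40 v 61% has 77.9% at 88 per arm but 75.2% at 90.

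**4. Bias, illustration only.** Assume 50% response in both arms, 100 per arm, and 6 leavers who would respond at 20%.
- All 6 in the patch arm: (50 − 6×0.2)/94 = 51.9% v 50%, a bias of +1.9 points.
- 4 patch, 2 control: (50 − 4×0.2)/96 − (50 − 2×0.2)/98 = 51.25% − 50.61% = +0.6.
- 3 and 3: 0. All 6 in the control arm: −1.9.
- Leavers who would respond at 80% reverse the signs: (50 − 6×0.8)/94 = 48.1% if all are in the patch arm, a bias of −1.9. At 50% the bias is 0.

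**The case against.** The strongest case against has four parts.

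First, the group is small. Diary-based exits before Visit 2 would need an unscheduled check, a missed visit before Day 5 cannot occur, and the only anticipated adverse event is minor skin irritation, managed by taking the patch off without leaving the study. This stands, and it limits the point.

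Second, the main lever is the analysis rule. Leavers are lost because the primary population requires the Day 5 rating and nothing covers its absence; counting them as non-responders would keep them in at no cost in visits. This also stands. But an assumed outcome is a poorer substitute for a rating the subject was willing to give, so the two remedies complement each other.

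Third, the exit diary might be entered on the Visit 2 form and be counted. The Study Day column of SAP Table 3 excludes that on a strict reading, and the value would in any case be an earlier rating.

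Fourth, subjects whose well-being is at risk should not be pressed to continue. That is right, and the remedy needs an investigator opt-out.

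The difference between 6.4.7 (subjects exit) and 7.11.1 (they may be withdrawn) is editorial, and the point does not rest on it.

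**Conclusion.** The point holds as a cheap improvement to data collection. The stated rules give up a primary rating that some leavers could still provide, and collecting it would bring the primary comparison closer to as-randomised.

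A reader might infer more than the documents support:
- *That the trial is underpowered because of these exits.* The 10% loss is budgeted.
- *That recovering leavers would add power.* The sign of the effect depends on how they would respond, and the documents do not say.
- *That the result is biased towards the patch.* Exits by arm, and how leavers would respond, are not given. In the illustration the bias runs from −1.9 to +1.9 points and is zero when exits are balanced. Larger figures can be produced: if 15% of the patch arm and 5% of controls leave, all would-be non-responders, with a true 60% in both arms, the bias is 0.60/0.85 − 0.60/0.95 = 70.6% − 63.2% = 7.4 points. Nothing in the documents supports those inputs.
- *That poor diary completion or patch removal will remove many subjects.* The visit schedule makes early diary-based exits unlikely, and patch removal is not an exit. The protocol does not say outright, however, that subjects who stop the patch stay on schedule.

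**What to change.** 1. In Protocol 6.4.7, remove diary non-compliance as an exit reason and record it as a protocol deviation.
2. In Protocol 7.11, state that subjects who stop the patch, or who are withdrawn for an adverse event or by the investigator, are asked to give the Day 5 Visit 2 rating and take the Day 6 call, unless they refuse or the investigator judges it unsafe.
3. Record any earlier exit assessment with its actual study day, and state in the SAP that it is not analysed as Day 5.

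The cost is wording plus a few visits and calls that are already planned, with the full dropout allowance of about 20 subjects as a ceiling. Some leavers will decline, so part of the loss remains and the SAP still needs a rule for a missing Day 5 rating.
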